- B If a site is not able to administer FLT201 the Sponsor will attempt to identify an alternative site for the infusion week only.
- C Height (screening only) and weight will also be measured.
- D Vital signs include pulse, blood pressure, respiratory rate, and temperature.
- E Participants will complete BPI-SF questionnaire once a day covering the 7 days following each screening visit, and then for 7 consecutive days, on each occasion commencing at the start of Weeks 4, 12, 24 and 37 post-treatment (week prior to the 38-week visit). Study sites will contact participants at the beginning of Week 37 to remind them to complete the questionnaires during Week 38.
- F Participants will complete the FACIT-Fatigue questionnaires at the end of each week during the screening period, and then at the end of Weeks 4, 12, 24, and 37 post treatment.
- G A weight-based tapering immunosuppressive regimen will be initiated at the Week 3 visit. Cohort 1 may not require immunosuppression. For details see the pharmacy manual.
- H Serum pregnancy test performed only at Week 1 to EOS and unscheduled visits if the urine pregnancy test is positive.
- I Testing to be performed twice weekly (including the testing as part of the scheduled study visit), initially commencing at Week 1 and concluding at the end of Week 9 and later commencing at Week 28 and concluding at the end of Week 38/EOS. The tests should be as evenly spaced through the week as possible, for example: Monday and Thursday, or Tuesday and Friday.
- J Testing to be performed three times weekly (including the testing as part of the scheduled study visit), commencing at Week 10 and concluding at the end of Week 27. The tests should be as evenly spaced through the week as possible, for example Monday, Wednesday, and Friday.
- K Local testing. Weekly CMV PCR testing for the duration the participant is taking tacrolimus in the immunosuppressant regimen. Tests should be undertaken to coincide with use of tacrolimus if outside of the prophylactic regimen. CMV IgG testing followed by CMV PCR. CMV PCR only indicated for a positive CMV IgG.
- L Local testing. Tacrolimus levels should be tested twice weekly until levels are in the therapeutic range and weekly thereafter for the duration the participant is taking tacrolimus in the immunosuppressant regimen. Tests should be undertaken to coincide with use of tacrolimus if outside of the prophylactic regimen.

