10.4 Immunosuppression Management

As noted in Section 6.5.3.1, liver-directed gene therapy with an AAV-based capsid has been reported to be associated with a likely T-cell mediated immune response to vector-transduced hepatocytes resulting in rises in liver transaminase levels, most notably ALT.

For all participants, LFTs will be closely monitored (Section 12.2.1) to enable timely identification and treatment of episodes of breakthrough ALT increase to preserve GCase expression (activity and concentration).

Participants will receive a prophylaxis regimen (post-dosing with FLT201) starting at approximately Week 3 post-dosing, continuing for a duration of up to approximately 3 weeks at the initial dose followed by a taper over 11 to 13 weeks.

The prophylaxis regimen consists of oral steroid (prednisolone/prednisone) and/or oral tacrolimus. An appropriate quantity of steroid and/or tacrolimus will be dispensed to the participant to cover the period between clinic visits and usage will be monitored via tablet counts.

In the event of breakthrough elevation of liver transaminase, participants will be assessed by the treating physician, and a reactive regimen (consisting of IV methylprednisolone) may be initiated in accordance with the CIMP.

The CIMP provides detail of the prophylaxis and reactive regimens, as well as more detailed guidance regarding the assessment and management in case of observed ALT elevation. The CIMP will be available to the investigator, pharmacy, and key study personnel. If the investigator considers that any systemic immune-modifying medication other than those prescribed in accordance with the CIMP may be necessary, this should be discussed with the Medical Monitor and Sponsor.

Any significant changes in the CIMP will be reviewed by the DMC, and changes may be issued as an update to the CIMP and communicated to all sites. If the DMC considers that significant changes are required, such as addition of other drugs (i.e., additional NIMP), then a protocol amendment may also be submitted.

11 Concomitant Medication

All non-study treatment received within 30 days prior to initial informed consent and for the duration of the study must be recorded on the appropriate eCRF page. Concomitant medication includes prescription and non-prescription medication and herbal treatments. Concomitant medication also includes immunosuppressants used as part of an immune management and monitoring regimen as described in the CIMP.

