12.2 Follow-up Visits (Weeks 1-32)

The following assessments will be conducted at each visit (or as specified):

- Concomitant medication status.
- Gaucher disease severity (GD-DS3) – Weeks 12 and 24.
- Physical examination.
- Vital signs (pulse, blood pressure, respiratory rate, and temperature).
- 12-lead ECG – Weeks 1, 4, 12, and 24.
- Urine pregnancy test (serum confirmation if positive urine test) – Weeks 1, 4, 8, 12, 16, 20, 24, and 32
- AE status.
- LFTs (local laboratory analysis).
- Abdominal and bone MRI – Weeks 12 and 24.
- Chest x-ray and pulmonary function tests – Weeks 12 and 24.
- Participants will be asked to complete an electronic diary commencing at Weeks 4, 12, and 24, completing the following questionnaires:
 - BPI-SF during the last 24 hours –daily for 7 consecutive days commencing at the start of each specified week.
 - FACIT-Fatigue completed at the end of the specified weeks.

Participants will be issued with instructions on electronic diary completion.

- For the duration a participant is on immunosuppression:
 - tacrolimus trough levels should be measured twice weekly until desired levels are established and weekly thereafter in conjunction with immunosuppressant dosing. See the Immunosuppression Management Plan for further information.
 - For participants positive for CMV IgG at screening, weekly CMV PCR testing should be conducted. Management guidelines in the case of CMV reactivation can be found in [Appendix 2: Management Guidelines for CMV Reactivation](#).
- Blood samples to evaluate (central laboratory analysis):
 - AAVS3 immune response – Weeks 1, 2, 6, 12 and 24.
 - Haematology, chemistry (including hs troponin-T and LFTs).

- Lyso-Gb1 – Weeks 4, 8, 12, and 24.
- Chitotriosidase, CCL18, bsALP, osteocalcin – Weeks 4, 12, and 24.
- GCase activity level.
- GCase concentration – Weeks 1, 2, 3, 6, 12, and 24.
- GCase immune response – Weeks 1, 2, 3, 6, 12, and 24.
- Research plasma sample.
- Plasma, saliva, urine, stool, (and semen, male participants only) samples for PCR of vg (three times within 7-10 days after FLT201 infusion then at separate visits). Collection of a particular matrix sample, e.g., plasma, can be stopped once negative results have been reported in that matrix at three consecutive visits at least 1 week apart after Week 1. Collection of the remaining matrices should continue until each delivers negative results at three consecutive visits at least 1 week apart after Week 1.

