12.2.1 Additional Laboratory Monitoring During Weeks 1-38/EOS

In addition to the main study site visits, participants will need to have additional laboratory assessments conducted from Week 1 until the end of Week 38/EOS to monitor for transaminitis (LFTs) and CMV reactivation, and to monitor tacrolimus levels, if required. In the event of suspected transaminitis (i.e ALT elevation), additional local LFT samples should be taken until the episode has resolved. In this situation, one additional sample for GCase activity level should be taken.

Frequency

- LFTs
 - From Week 1 to the end of Week 9, and from Week 28 to the end of Week 38/EOS, the additional laboratory assessments will be conducted once per week if there is already a scheduled study visit during the week, and twice per week if there is no scheduled study visit during the week.
 - From Week 10 to the end of Week 27 the additional LFT laboratory assessments will be conducted twice per week if there is already a scheduled study site visit during the week, and 3 times per week when there is no scheduled study site visit during the week.
 - The study site visit (when applicable) and additional laboratory assessments should be evenly spaced through the week.
- GCase plasma activity
 - In the event of raised LFTs, an additional GCase sample should be taken once per week during the additional laboratory assessments until the episode has resolved.

Sample Collection

These additional samples may be taken at study site or at an alternative location (e.g., participant's home) by a home nursing vendor, in these instances the participant's vital signs will be measured prior to completing the blood draw.

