12.5 Study Procedures/Evaluations

All study assessments will be conducted in accordance with the study schedules.

- [Table 1: Schedule of Assessments](#)
- [Table 2: Detailed Schedule of Assessment for Day -1 to Day 3 \(Infusion Week\)](#)

For all central laboratory samples, the procedures for collection, processing, storing, and transporting to the central laboratory are fully described in the study Laboratory Manual.

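### Table 1 footnote K ties weekly CMV PCR to tacrolimus, Protocol 12.2 ties it to immunosuppression, and tacrolimus-free weeks could go untested

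*Protocol*

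**What the plan says.** **Table 1, footnote K.** The duration of testing is given as "Weekly CMV PCR testing for the duration the participant is taking tacrolimus in the immunosuppressant regimen". The next sentence repeats the tacrolimus link for use outside the prophylactic regimen. The footnote then limits PCR by serology: "CMV IgG testing followed by CMV PCR. CMV PCR only indicated for a positive CMV IgG".

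**Protocol 12.2.** Under the lead-in "For the duration a participant is on immunosuppression", one bullet reads "For participants positive for CMV IgG at screening, weekly CMV PCR testing should be conducted". The bullet beside it, under the same lead-in, covers tacrolimus trough levels.

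**Protocol 12.2.1.** Additional laboratory assessments run from Week 1 to the end of study "to monitor for transaminitis (LFTs) and CMV reactivation, and to monitor tacrolimus levels, if required".

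**Protocol 12.5.3.** When immunosuppressants are used at any other time, tacrolimus monitoring and CMV testing (if required) go with the immunosuppressant dosing and continue for two weeks after it stops.

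**Protocol 10.4.** "The prophylaxis regimen consists of oral steroid (prednisolone/prednisone) and/or oral tacrolimus". For breakthrough transaminase elevation, "a reactive regimen (consisting of IV methylprednisolone) may be initiated in accordance with the CIMP".

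**Protocol 12.5.** "All study assessments will be conducted in accordance with the study schedules". The schedules named there are Tables 1 and 2.

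**The concern.** One safety test has two triggers in the current text. A site that works from the schedule table, as 12.5 directs, could stop CMV PCR when tacrolimus stops, or never start it if the regimen is steroid alone. A site that works from 12.2 would continue.

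The participants concerned can be enrolled. Exclusion criterion 7 removes only people who are both IgG-positive and PCR-positive at screening, so someone who is IgG-positive and PCR-negative may be dosed and then immunosuppressed.

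Appendix 2 is where the missing test would matter. A titre above 3000 genomes/mL (or a local cut-off) calls for the immunosuppression regimen to be re-evaluated whether or not there are symptoms. In a week without a PCR, that trigger has nothing to act on. Appendix 2 also says that reactivation is much less frequent in this kind of setting than after transplantation, so the stake is early detection of an uncommon event.

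**Working it through.** The plan states no number of CMV PCRs, so there is no figure to reproduce. The check compares the two rules and counts the weeks on which they differ.

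**1. The rules side by side**

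| | Footnote K | Protocol 12.2 | Protocol 12.5.3 (other times) |
|---|---|---|---|
| Who | IgG-positive | IgG-positive at screening | If required |
| Exposure | Tacrolimus | Immunosuppression | Immunosuppressant dosing |
| Frequency | Weekly | Weekly | Not stated |
| After stopping | Nothing stated | Nothing stated | Two more weeks |

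K and 12.2 agree on serology and frequency. They differ on the exposure.

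**2. Length of prophylaxis (Protocol 10.4)**

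Prophylaxis starts at about Week 3, with up to about 3 weeks at the initial dose and then a taper of 11 to 13 weeks.

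- Shorter taper: 3 + 11 = 14 weeks (Weeks 3 to 16).
- Longer taper: 3 + 13 = 16 weeks (Weeks 3 to 18).

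Because the initial phase is an upper limit, 14 to 16 is an approximate maximum.

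**3. PCR counts for an IgG-positive participant**

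Let D be the weeks on any immunosuppression and T the weeks on tacrolimus. At one PCR a week, 12.2 gives D, literal K gives T, and the gap is D − T.

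- Tacrolimus throughout: T = D, gap 0.
- Tacrolimus stopped s weeks before the steroid: gap s.
- Steroid alone: T = 0, so the gap is 14 − 0 = 14 or 16 − 0 = 16.

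**4. Reactive treatment**

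For IV methylprednisolone alone, literal K gives no PCR. Section 12.2 gives weekly PCR while treatment lasts, and 12.5.3 adds two weeks, subject to its own qualifier. The duration is left to the CIMP, so no count is possible.

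**5. Blood draws already scheduled**

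Footnotes I and J set local liver tests twice weekly to Week 9 and three times weekly from Week 10 to Week 27.

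- Weeks 3 to 16: 7 × 2 + 7 × 3 = 35 draws.
- Weeks 3 to 18: 7 × 2 + 9 × 3 = 41 draws.

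Every week of prophylaxis therefore already has at least two local draws.

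**The case against.** The strongest reply is that the tacrolimus condition is deliberate and that 12.2 takes it for granted. The neighbouring bullet in 12.2 asks for tacrolimus troughs under the same lead-in, without saying that they apply only to people taking tacrolimus. Read literally, it would order drug levels in participants not on the drug, so immunosuppression in that passage may simply mean a tacrolimus-containing regimen. Section 12.5.3 pairs the two tests in the same way, and the closing qualifier in 12.2.1 may cover CMV as well. Footnote K states the tacrolimus link twice and is worded in parallel with footnote L. Section 6.5.3.2 lists CMV susceptibility under tacrolimus, and its corticosteroid list names no infection risk.

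Much of this stands. It means the documents cannot settle which text is the intended one. It does not remove the conflict. Section 6.5.3.2 also has a general line on CMV reactivation, Appendix 2 speaks of immunosuppression without naming an agent, and a site reading 12.2 as written finds no tacrolimus condition. If K is right, 12.2 is the text that needs correcting.

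Three stronger readings are tempting and are not supported:

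- *The protocol leaves steroid-treated participants without CMV surveillance, or some have already missed tests.* Section 12.2 covers them on its plain reading. Section 10.4 permits steroid-only regimens but does not show that anyone receives one, and the CIMP is not among the documents. Section 12.5 does not say that the tables override 12.2.
- *The 12.2 tests are mandatory.* The verb there is should.
- *An intermediate shortfall can be read from the visit marks in the CMV row of Table 1.* Column positions in the available copy are unreliable: matching 12.2 takes a shift of one column for the MRI row and two for the urine pregnancy row. No count from those marks is used here.

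**Conclusion.** The inconsistency is real and lies in the current protocol text. For an IgG-positive participant on steroid-only prophylaxis, the two rules differ by up to about 14 to 16 weekly PCRs (0 against 14 to 16). For a participant whose tacrolimus ends early, they differ by the tacrolimus-free weeks. With tacrolimus throughout, they agree during dosing.

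This rests on three assumptions: footnote K is applied literally, 12.2 is read plainly, and a full course is given. The number of people affected is unknown and may be zero. Besides the missing CIMP, footnote G says that Cohort 1 may need no immunosuppression at all.

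Severity is minor. SAP 9.6.2 only lists CMV results, so no endpoint, sample size or analysis changes. It is still worth correcting, because it concerns a safety test and the correction is one footnote.

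**What to change.** Ask the sponsor which exposure is meant to trigger testing.

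- **Preferred:** reword footnote K to call for weekly CMV PCR in participants who were CMV IgG-positive at screening, for as long as they receive any immunosuppression under the CIMP. Add a cross-reference to 12.5.3 for use outside prophylaxis, including the two weeks after cessation.
- **If the tacrolimus condition is intended:** state it in 12.2 and 12.5.3, with the reason, and leave K as it is.

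**Cost of the preferred change.** Relative to the plain reading of 12.2, no test is added during prophylaxis. Relative to literal K, it adds at most about 14 to 16 local PCRs per affected participant over a full prophylaxis course. These can be taken at the liver-test draws already scheduled, so no extra visit is needed.

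If dosing is already over, rewording no longer helps those participants. The sponsor can then look for tacrolimus-free weeks without a PCR using the immunosuppressant log (Protocol 10.3), the immunosuppressant dose plots (SAP 7.2.2) and the CMV listing (SAP 9.6.2).

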6.1 Background

Gaucher disease is an inherited autosomal recessive disease caused by deficient activity of the lysosomal enzyme, glucocerebrosidase (GCase), and the resultant accumulation of its undegraded substrate, glucosylceramide (GL1), and other glycolipids [Pastores 2000]. The disease has a prevalence of 1:40,000 to 1:60,000 [Stirnemann 2017] and is classified by three main phenotypes delineated by the absence (type 1) or presence (type 2 and type 3) of primary CNS involvement [Pastores 2000]. Gaucher disease is caused by mutation in the β -glucosylceramidase gene (*GBA1*), on chromosome 1q22 (GBA; 606463), encoding the enzyme GCase, resulting in deficiency in GCase activity and accumulation of GL1 in cells of the macrophage-monocyte system [Sidransky 2012].

The clinical manifestations of Gaucher disease reflect chronic, progressive macrophage tissue infiltration and Gaucher cell deposition in the spleen, liver, bone marrow, and other tissues resulting in splenomegaly, hepatomegaly, and the signs and symptoms associated with thrombocytopenia, anaemia, and bone involvement. Bone involvement can include acute and chronic pain, as well as osteonecrosis, osteopaenia, and osteoarthritis. Lung involvement and massive lymphadenopathy are less frequent.

The standard of care for Gaucher disease is long-term parenteral enzyme replacement therapy (ERT), which aims to increase the level of functional GCase enzyme, or oral substrate reduction therapy (SRT), which aims to reduce the amount of GL1 that is produced. Although many patients achieve clinically meaningful benefit within 2-5 years of treatment, response can be variable and incomplete. Platelet counts in some patients may be poorly responsive and, additionally, bone disease may sometimes progress despite otherwise successful treatment.

ERT consists of long-term, parenteral administration of recombinant GCase every 2 weeks. Current ERTs include Cerezyme[®] (imiglucerase), VPRIV[®] (velaglucerase), and Elelyso[®] (taliglucerase), with Elelyso not available in the European Union (EU).

SRT is a long-term oral medication but may be limited to specific populations; patients for whom ERT is not suitable Zavesca[®] (miglustat) or patients who are not CYP2D6 ultra-extensive metabolisers Cerdelga[®] (eliglustat).

There are currently no licensed advanced therapy investigational medicinal products (ATIMPs) available for the treatment of any form of Gaucher disease.

6.2 FLT201

FLT201 is an investigational ATIMP intended for the treatment of Gaucher disease. The FLT201 product is a single-stranded (ss) adeno-associated viral vector serotype S3 (AAVS3) and contains AAV and the human *GBA1* gene.

The FLT201 AAV construct has three major features:

1. A novel engineered capsid (AAVS3) which has been selected based on its ability to transduce human hepatocytes with a high efficiency and more effectively than other capsids.
2. A codon-optimised transgene (*GBA1*) under the control of a liver-specific promoter (LSP), FRE76.

- It encodes a protein engineered GCase (variant 85), which incorporates two amino acid (AA) substitutions that should result in a putative disulfide bond (S-S) in the GCase protein structure.

The AA substitutions are internal and involve no exposed residues. Changes are not predicted to affect the active site, the external structure, or the overall charge of GCase.

The construct for FLT201 is represented in [Figure 1](#).

Figure 1: Schematic Representation of the FLT201 Construct for Gaucher Disease

Abbreviations: bGHpA=bovine growth hormone polyadenylation signal; bp=basepairs; FRE76=liver-specific promoter; GBAco-var85=codon-optimised β-glucocerebrosidase engineered for increased stability (variant 85); ITR=inverse terminal repeat; SV40i=SV40 intron; white box=protein coding sequence.

Freeline developed FLT201 encoding GCase (variant 85) since the wild type GCase displays a short half-life when exposed to physiological pH. GCase (variant 85) displays increased protein stability in various physiological matrices compared to the wild type GCase.

Following receptor-mediated uptake of AAV into the hepatocytes, transgenes are expressed by host cell transcription machinery [[Mingozzi 2011](#)]. Under the control of the LSP, the GBA1 gene will be expressed in host hepatocytes leading to the production and secretion of a functional GCase protein into the blood circulation. As GCase is produced in host hepatocytes, glycosylation will be host specific and thus be less likely than an exogenous protein to be recognised as foreign [[Mingozzi 2003](#)].

FLT201 is, therefore, anticipated to lead to continuous endogenous production of GCase (variant 85) in hepatocytes, resulting in steady plasma activity levels, and thus has the potential to provide enhanced uptake of the active enzyme by macrophages and better penetration into the target tissues of Gaucher disease.

6.3 Nonclinical Data

The overall nonclinical development programme consists of in vitro and in vivo pharmacodynamic studies, and in vivo proof of concept study in GBA-deficient mice and a single-dose GLP-compliant toxicology/biodistribution study in mice (C57BL/6) and a single-dose long-term investigational study in non-human primates (NHP) (rhesus macaques). Nonclinical studies showed the FRE76 promoter is liver specific and that the AAVS3 capsid is efficient at transducing human hepatocytes. The in vitro and humanised liver mouse model (FRG) studies demonstrated that transduction of murine hepatocytes (but not human hepatocytes) by AAV2/8 (AAV8) is efficient, whereas transduction of human hepatocytes by AAVS3 (but not murine hepatocytes) is very efficient. Studies in mice to test the therapeutic benefit of FLT201 genome were, therefore, performed with AAV8 capsid pseudotyped constructs. In GBA-deficient mice, following the administration of AAV2/8 pseudotyped FLT201 genome, plasma GCase activity level increased, resulting in normalisation of the biomarker glucosylsphingosine (Lyso-Gb1); the deacylated lysolipid of GL1 and the substrate for the GCase enzyme. In vitro studies demonstrated that GCase variant 85 when presented to human PBMCs or macrophages can be taken up in a dose-dependent manner similar to ERT.

Please refer to the FLT201 Investigator's Brochure (IB) for full details of the nonclinical data.

